2.1.1.5 Post-baseline measurement

Post baseline measurements are defined as those assessments after the start of study treatment.

2.1.1.6 Visit remapping and assessment windows

Since the actual visit for a subject may not exactly coincide with their targeted visit date, the actual visit date is mapped to a study visit. Also note that month 6 is equivalent to week 24, and month 12 is equivalent to week 52.

The next study day window will be utilized to define study visit for lab, vital signs, C-SSRS and [REDACTED] PROs collected during office visits [REDACTED] before dose is administered.

Table 2-1 Study visit windows

Study visit	Target Day	Study Day
Baseline	Please refer to Section 2.1.1.4 .	
Week 4	28	16-43

Week 8	56	44-71
Week 12	84	72-99
Week 16	112	100-127
Week 20	140	128-155
Week 24	168	156-183
Week 28	196	184-198
Week 32	224	199-239
Week 36	252	240-267
Week 40	280	268-295
Week 44	308	296-323
Week 48	336	324-351
Week 52	364	352-379
Safety follow up	Safety follow-up should be excluded from the analysis visit windows described above and summarized under 'safety follow-up' for safety analyses only. Refer to Table 2.2 .	

Note: xx: target day then study day window: (xx-12 days) up to (xx+ 15 days)

For efficacy parameters: If more than one visit (including the unscheduled visits) fall within the same defined window with non-missing measurements, scheduled visit will be used regardless of the distance from the target day. Unscheduled visit will only be used when there is no measurement from scheduled visit in the defined window. The closest visit to the target day among the same type of visit (i.e., closest of all scheduled visits or if no scheduled visits, closest of all unscheduled) will be considered for analysis. If two assessment dates are equidistant from the target date, the latter assessment will be considered for analysis. The exception is an assessment at early study withdrawal visits along with another assessment within a window. In such cases the early-withdrawal assessment will be used.

For safety parameters: in case of competing assessments within a analysis window, the last one closest to the scheduled visit day will be used.

Table 2-2 Study intervals for safety analysis

	Start time point	End time point

Core phase	Treatment start date	
 1. Subject completes 52 weeks on core phase treatment i.e. if trt disposition reason is “COMPLETED” on DS domain 
 a. If subject does not enter PTA phase then use week 52 visit date b. If subject enters PTA phase then 
 i. Subject enters PTA on week 52 visit date then use a day prior to week 52 visit date ii. Subject enters PTA phase after week 52 then use week 52 visit date 2. Subject completes 52 weeks on core phase but discontinues treatment early i.e. core phase treatment disposition reason is not equal to “COMPLETED” on DS domain 
 a. If subject does not enter PTA phase 
 i. if week 52 visit date > treatment end date plus 27/1 day then use treatment end date plus 27/1 day ii. if week 52 visit date <= treatment end date plus 27/1 day then use week 52 visit date b. If subject enters PTA phase 
 i. if week 52 visit date > treatment end date plus 27/1 day then use treatment end date plus 27/1 day ii. if week 52 visit date <= treatment end date plus 27/1 day then use a day prior to first dose in PTA phase 3. Subject discontinues treatment early and does not complete 52 weeks on core phase i.e. core phase trt disposition reason is not equal to “COMPLETED” on DS domain and Week 52 visit date is not available in SV domain and study disposition reason is equal not to “COMPLETED” on DS domain 
 a. If treatment disposition date > treatment end date plus 27/1 day then use treatment end date plus 27/1 day b. If treatment disposition date <= treatment end date plus 27/1 day then use treatment disposition date
Safety follow up	Core phase end plus 1 day	
 a) If subject does not enter PTA phase then use study disposition date; b) If subject enters PTA phase then use a day prior to first dose in PTA phase
PTA phase	First erenumab injection	
 1. If subject completes 52 weeks on PTA phase then use min (trt disposition or study disposition date)

	date in PTA phase	
2. If subject discontinues prior to completing 52 weeks on treatment in PTA phase i.e. treatment disposition reason is not equal to “COMPLETED” on DS domain then
 
 If treatment disposition date > treatment end date plus 27 day then use trt end date plus 27 day If treatment disposition date <= treatment end date plus 27 day then use trt disposition date
--	-------------------	--

	Start time point	End time point
Initially assigned treatment (IAT) period (core phase)	Treatment start date	
1. Subject completes 52 weeks on IAT i.e. core phase treatment disposition reason is “COMPLETED” and week 52 visit date is non-missing in SV domain and date of switching is missing on DS domain
 
 If subject does not enter PTA phase then use week 52 visit date from SV domain If subject enters PTA phase then 
 i. Subject enters PTA on week 52 visit date then use a day prior to week 52 visit date ii. Subject enters PTA phase after week 52 then use week 52 visit date 
2. Subject completes 52 weeks on core phase but permanently discontinues IAT early i.e. trt disposition reason is not equal to “COMPLETED” on DS domain and week 52 visit date is non-missing in SV domain and date of switching is missing on DS domain
 
 If subject does not enter PTA phase 
 i. if week 52 visit date > treatment end date plus 27/1 day then use treatment end date plus 27/1 day ii. if week 52 visit date <= treatment end date plus 27/1 day then use week 52 visit date If subject enters PTA phase 
 i. if week 52 visit date > treatment end date plus 27/1 day then use treatment end date plus 27/1 day

		
 ii. if week 52 visit date \leq treatment end date plus 27/1 day then use a day prior to first dose in PTA phase 3. Subject does not complete 52 weeks on study and permanently discontinues IAT i.e. week 52 visit date is missing in SV domain and date of switching is missing on DS domain and core phase treatment disposition reason is not equal to "COMPLETED in DS domain then use min(trt disposition date, trt end date plus 27/1 day) 4. Subject switches IAT then use day prior to date of first switch on DS domain
Switched treatment period (core phase)	Date of first switch on DS domain	
 1. Subject completes 52 weeks on switched treatment i.e. core phase treatment disposition reason is "COMPLETED" and week 52 visit date is non-missing in SV domain 
 a. If subject does not enter PTA phase then use week 52 visit date from SV domain b. If subject enters PTA phase then 
 i. Subject enters PTA on week 52 visit date then use a day prior to week 52 visit date ii. Subject enters PTA phase after week 52 then use week 52 visit date 2. Subject completes 52 weeks on core phase but discontinues switched treatment early i.e. core phase trt disposition reason is not equal to "COMPLETED" on DS domain 
 a. If subject does not enter PTA phase 
 i. if week 52 visit date $>$ treatment end date plus 27/1 day then use treatment end date plus 27/1 day ii. if week 52 visit date \leq treatment end date plus 27/1 day then use week 52 visit date b. If subject enters PTA phase 
 i. if week 52 visit date $>$ treatment end date plus 27/1 day then use treatment end date plus 27/1 day ii. if week 52 visit date \leq treatment end date plus 27/1 day then use a day prior to first dose in PTA phase 3. Subject does not complete 52 weeks on switched treatment i.e. core phase trt disposition reason is not

		equal to “COMPLETED” on DS domain and week 52 visit date is missing in SV domain then use min(treatment disposition date, treatment end date plus 1 day)
--	--	--

Note: DS: Disposition domain; SV:Visit domain; IAT: Initially assigned treatment

Monthly interval for efficacy endpoints (from ediary)

Monthly efficacy measurements will be calculated based on the subject's starting dose and visit schedule defined below using eDiary data collected from beginning of the baseline phase (week -4 visit) up to week 52 visit if subjects do not have safety follow up visit. For subjects with safety follow up, consider data up to the safety follow-up visit. The algorithm remains the same for initially assigned treatment and switched treatment. ediary data will be collected during core phase only and will not be collected during extension phase.

Table 2-3 Study intervals for efficacy endpoints – Erenumab and Oral prophylactics

Study phase	Assessment Time point	Interval based on dose dates	
		Start date	End date
Baseline period	Baseline	From ediary device assignment date (or week -4 visit)	Day prior to study day 1
Treatment Period	Week 4	Study day 1	
• Week 4 visit date - 1• Study day 1 + 27 days if Week 4 visit is missed 
Note: if day 1 dose is the last dose subject received, the rest of monthly rates during treatment period will be calculated based on consecutive 28-day interval beginning

	Week 8	
• Week 4 visit date• Week 4 analysis visit end date + 1 day if Week 4 visit is missed	
• Week 8 visit date – 1• Week 4 analysis visit start date + 27 days if Week 8 visit is missed
	Week 12	
• Week 8 visit date• Week 8 analysis visit end date + 1 day if Week 8 visit is missed	
• Week 12 visit date – 1• Week 12 analysis visit start date + 27 days if Week 12 visit is missed
	Week 16	
• Week 12 visit date	
• Week 16 visit date – 1

		
 • Week 12 analysis visit end date + 1 day if Week 12 visit is missed 	
 • Week 16 analysis visit start date + 27 days if Week 16 visit is missed
	Week 20	
 • Week 16 visit date • Week 16 analysis visit end date + 1 day if Week 16 visit is missed 	
 • Week 20 visit date – 1 • Week 20 analysis visit start date + 27 days if Week 20 visit is missed
	Week 24	
 • Week 20 visit date • Week 20 analysis visit end date + 1 day if Week 20 visit is missed 	
 • Week 24 visit date – 1 • Week 24 analysis visit start date + 27 days if Week 24 visit is missed
	Week 28	
 • Week 24 visit date • Week 24 analysis visit end date + 1 day if Week 24 visit is missed 	
 • Week 28 visit date – 1 • Week 28 analysis visit start date + 27 days if Week 28 visit is missed
	Week 32	
 • Week 28 visit date • Week 28 analysis visit end date + 1 day if Week 28 visit is missed 	
 • Week 32 visit date – 1 • Week 32 analysis visit start date + 27 days if Week 32 visit is missed
	Week 36	
 • Week 32 visit date • Week 32 analysis visit end date + 1 day if Week 32 visit is missed 	
 • Week 36 visit date – 1 • Week 36 analysis visit start date + 27 days if Week 36 visit is missed
	Week 40	
 • Week 36 visit date • Week 36 analysis visit end date + 1 day if Week 36 visit is missed 	
 • Week 40 visit date – 1 • Week 40 analysis visit start date + 27 days if Week 40 visit is missed
	Week 44	
 • Week 40 visit date • Week 40 analysis visit end date + 1 day if Week 40 visit is missed 	
 • Week 44 visit date – 1 • Week 44 analysis visit start date + 27 days if Week 44 visit is missed
	Week 48	
 • Week 44 visit date • Week 44 analysis visit end date + 1 day if Week 44 visit is missed 	
 • Week 48 visit date – 1 • Week 48 analysis visit start date + 27 days if Week 48 visit is missed
	Week 52	
 • Week 48 visit date • Week 48 analysis visit end date + 1 day if Week 48 visit is missed 	
 • MIN (Week 48 visit date + 27, EoS) 
MIN (Week 52 analysis visit start date + 27 days if Week 48 visit is missed, EoS)

Where EoS date is the date of the end of study visit.

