6.6 Additional treatment guidance

6.6.1 Treatment compliance

Core Phase

Erenumab medication is administered by the investigator or designated study staff at each visit. This information should be captured in the source document and the eCRF at each visit. All erenumab dispensed and returned must be recorded in the Drug Accountability Log. Site staff will review eDiary compliance with the patient at each visit, when applicable.

For SoC oral prophylactics, the investigator must promote compliance by instructing the subject to take the study treatment exactly as prescribed and by stating that compliance is necessary for the subject's safety and the validity of the study. The subject must also be instructed to contact the investigator if he/she is unable, for any reason, to take the study treatment as prescribed. Compliance will be assessed by the investigator and/or study personnel at each visit using pill counts (if applicable) and information provided by the subject. This information should be captured in the source document at each visit. SoC oral prophylactics prescribed and used must be recorded in the Drug Accountability Log for Standard of Care, to allow proper reimbursement by Novartis.

Extension Phase

After completion of the Core Phase (Week 52 Visit, [Table 8-1](#)) patients will be administered study drug at the study site (Week 52 Visit) and will then be required to have quarterly study visits at the study site. Between the quarterly visits patients will have study drug injections every 28 days either 1) administered by the site staff at brief injection visits at site or 2) self-administered at home with documented on-site training for correct injection procedure.

Note: If study drug is provided to the patient for self-administration, the patient will need to be properly trained with required documentation filed in the patient's source documents. The documentation will need to indicate that the patient was trained on the correct injection procedure, the proper drug storage and required steps for documenting the injection details including day of injection, dose location etc. The patient will then need to provide the site with the required documentation at each quarterly visit.

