Contact IRT	X	X	X	X	X	X	X	X	X	X	X	X	X	X	X	X	
Clinical Outcome Assessment(s) ⁶		X	X	X	X	X	X	X	X	X	X	X	X	X	X	X	X
Patients' Global Impression of Change						X				X			X		X		X

Period	Screening			Open Label Randomized Treatment													
	Visit Name	Screening	Baseline	Treatment	Week 4	Week 8	Week 12	Week 16	Week 20	Week 24	Week 28	Week 32	Week 36	Week 40	Week 44	Week 48	Week 52 / Early Exit ¹⁰
Days	Days	-42 to -28	-28 to -1	Day 1	28	56	84	112	140	168	196	224	252	280	308	336	364
Weeks	Weeks	-6 to -4	-4 to -1	1	4	8	12	16	20	24	28	32	36	40	44	48	52
Adverse Events ⁹				X	X	X	X	X	X	X	X	X	X	X	X	X	X
Serious Adverse Events ⁹	X	X	X	X	X	X	X	X	X	X	X	X	X	X	X	X	X
Concomitant medications	X	X	X	X	X	X	X	X	X	X	X	X	X	X	X	X	X
Concomitant therapies	X	X	X	X	X	X	X	X	X	X	X	X	X	X	X	X	X
Core phase ¹⁰ completion																	X

^x Assessment to be recorded in the clinical database or received electronically from a vendor

¹ Full exam at Screening, Week 52. Height and weight will be measured at full exam. Short physical exam at all other visits.

² Results of pregnancy tests (serum or urine) will be captured as source and not in eCRF.

³ For subjects randomized to SoC oral prophylactics, central blood chemistry must be done at Screening, Treatment, Week 24, Week 52. All other visits, central blood chemistry to be done as needed for monitoring. Any additional safety measurements, if applicable, should be implemented as per label.

⁴ C-SSRS will be the electronic C-SSRS designed for computer administration (web or phone)

⁵ At every monthly study visit, the investigator should assess tolerability to randomized treatment (erenumab or SoC oral prophylactics) and determine if switching is appropriate. At Week 48, this will be the last dose of erenumab for subjects randomized to erenumab (monthly treatment). SoC oral prophylactics will continue to be dosed through month 12 as per label.

⁶ Patients will record migraine, headache, and headache medication information daily using the provided electronic diaries.

⁹ AE to be captured from Day 1 onward and SAE collection will be captured after informed consent is obtained.

¹⁰ Patients that complete Core Phase visits through Week 52 may be eligible to enter the Extension Phase. All patients will receive erenumab during the Extension Phase.

Table 8-2 Assessment Schedule – Extension Phase

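### SAP Table 2-2 assigns the pre-dose Week 52 labs, ECG, vital signs and weight of treatment completers who start the extension that day to the extension phase, in conflict with Table 2-1 and the protocol

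*SAP*

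**What the plan says.** SAP 2.1.1.6 contains two sets of rules that both bear on a Week 52 safety assessment.

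- **Table 2-2** defines the study intervals for safety analysis by calendar date. For a subject whose core treatment disposition is COMPLETED there are three cases. Without extension: "If subject does not enter PTA phase then use week 52 visit date". With a later start: "Subject enters PTA phase after week 52 then use week 52 visit date". With a same-day start: "Subject enters PTA on week 52 visit date then use a day prior to week 52 visit date". The initially assigned and switched treatment periods repeat these rules. Safety follow-up starts at "Core phase end plus 1 day" and, for extension entrants, ends as follows: "If subject enters PTA phase then use a day prior to first dose in PTA phase". The PTA phase starts on the date of the "First erenumab injection" in that phase.
- **Table 2-1** maps assessments to visits by study day. Week 52 is days 352 to 379. The legible text applies it to labs, vital signs, C-SSRS and PROs taken before dosing. Part of that sentence is redacted and ECG is not legibly named. The only phase it excludes is safety follow-up.

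Same-day entry is the route described in Protocol 6.6.1: after the core phase, "patients will be administered study drug at the study site (Week 52 Visit"). Protocol Table 8-1 lists the Week 52 chemistry, ECG, vital signs and full examination (with weight) as core-phase assessments. Footnote 3 says of the oral arm that "central blood chemistry must be done at Screening, Treatment, Week 24, Week 52". Protocol 9.2 treats the core phase as completed once the Week 52 visit is completed.

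**The concern.** Read by date, Table 2-2 moves core assessments into a phase that this SAP leaves to a separate plan (SAP section 1). It does so for one group of completers only. Two subjects with identical core participation and identical Week 52 tests are classified differently according to whether the first extension injection was given that day.

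That matters because extension entry is selected, and selected differently in each arm. Protocol section 3 requires, in the investigator's opinion, benefit from erenumab in the erenumab arm and need for a treatment switch in the oral arm. If same-day entrants drop out of a Week 52 table, the erenumab column is depleted of subjects judged to benefit and the oral column of subjects judged to need a switch. The Week 52 comparison is then no longer between the randomized groups, or even between similarly selected parts of them.

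Week 52 is also not one visit among many for these data. Chemistry has only Weeks 24 and 52 as required post-baseline time points. Weight is measured only at full examinations, at Screening and Week 52 (Protocol Table 8-1 footnote 1 and Table 8-3), yet SAP 2.8.4.2 plans a summary of change from baseline in weight.

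**Working it through.** This is a question of date rules, so the check is to apply them.

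**Step 1: reproduce the plan's own window.** The note to Table 2-1 gives target day minus 12 to target day plus 15. For Week 52 (target day 364): 364 − 12 = 352 and 364 + 15 = 379. This matches the stated 352 to 379.

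**Step 2: apply Table 2-2 to a treatment completer with the Week 52 visit on study day 364.**

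| Extension start | Core phase ends | Safety follow-up | PTA starts | Phase of the Week 52 assessments, by date |
|---|---|---|---|---|
| None | 364 | from 365 | none | Core |
| 28 days later (day 392) | 364 | 365 to 391 | 392 | Core |
| Same day (day 364) | 364 − 1 = 363 | 363 + 1 = 364 to 364 − 1 = 363, empty | 364 | PTA |

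Visits on days 359, 369 and 379 give the same pattern. In every case the visit lies inside the Table 2-1 window for Week 52.

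**Step 3: check that the assessments precede the injection.** SAP 2.1.1.6 describes the windowed measurements as taken before dosing, and SAP 2.8.4.2 says the same of vital signs. Protocol 8.4.2 prefers ECG first, then vital signs, then blood sampling. Table 2-2 works on whole dates and makes no exception for pre-dose values. By contrast, SAP 2.1.1.4 does settle the equivalent same-day question at Day 1: the last value before first administration is baseline.

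**Step 4: compare with the protocol's safety period.** Protocol 12.5.2 runs the on-treatment period to 112 days after the last dose. With the last core erenumab dose at Week 48 (day 336), that is 336 + 112 = day 448, which covers day 364. SAP section 4 declares no change to protocol-specified analyses.

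**Step 5: identify the outputs at risk.** Lab summaries are by visit and initially assigned treatment (SAP 2.8.3). ECG and vital-sign summaries are by visit for initially assigned treatment (SAP 2.8.4.1 and 2.8.4.2). Table 2-2 is the SAP's only definition of that period for safety. If a programmer filters on it, the share of completers' Week 52 values omitted in an arm equals that arm's same-day entry proportion p, and 1 − p remains. The documents do not give p, so the range is 0 to 100% in each arm.

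**Step 6: who is covered.** The rule quoted applies to treatment completers. For an early discontinuer whose Week 52 visit falls after treatment end plus 27/1 days, the visit is outside core whether or not the extension is entered. For a subject who switched, the initially assigned period ended the day before the first switch, so only the switched period is affected.

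**The case against.** The best answer is that nothing need be lost. Table 2-1 maps pre-dose labs and vital signs to Week 52 by study day. The only phase it excludes is safety follow-up, which is empty for these subjects. The outputs are by visit, and no sentence requires an assessment also to fall inside a Table 2-2 interval. SAP 2.1 says analyses use all data up to the cut-off. SAP 2.1.1.5 defines post-baseline as after the start of treatment, with no end date, and that governs the counts of notable vital signs at any post-baseline visit. The day-prior rule is also sensible for adverse events, because an event starting on the first extension dose date cannot be separated from that dose by date alone.

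Most of this stands. It shows that a reasonable programmer could keep the data. It does not show that the SAP requires it: Table 2-1 assigns a visit label, not a phase or treatment period, and neither table is said to override the other. The absence of ECG from the legible Table 2-1 text proves little, given the redaction.

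A reader might infer that Week 52 safety data are certainly lost, or lost for most subjects. The documents support neither. They give no same-day entry rate. They foresee later entry because of approval delays, and protocol versions 0 and 1 had a follow-up period instead of an extension.

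**Conclusion.** The point holds as a conflict within the SAP and with the protocol. For treatment completers who start PTA at the Week 52 visit, Table 2-2 places pre-dose Week 52 labs, ECG, vital signs and weight in PTA by date. Table 2-1, Protocol 9.2, Protocol Table 8-1 and the rule for other completers all treat the visit as core. It is more than a missing detail, because the date rule is explicit and would misclassify core data in any output filtered by the Table 2-2 period.

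The consequence is conditional on that filter being used. If it is, the Week 52 summaries compare differently selected subsets of the arms, and weight loses its only scheduled post-baseline value for the subjects concerned. How many that is cannot be derived from the documents.

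The reach is limited to safety summaries. Efficacy has its own intervals (Table 2-3) and PGIC its own Month 12 rule (SAP 2.7.2 and 2.7.3), so neither is affected. Week 24 labs and vital signs through Week 48 are untouched. The conclusion assumes that the assessments are made before the injection, as the documents describe.

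**What to change.** Keep the day-prior rule for the onset of adverse events. Add one sentence to Table 2-2: lab, ECG, vital-sign and weight assessments taken at the Week 52 visit before the first PTA injection belong to the core phase, and to the treatment period (initially assigned or switched) that would otherwise have ended on the Week 52 visit date, whether or not the subject enters PTA that day.

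Because Table 2-2 uses whole dates, also say how pre-dose status is recognised. If clock times are not available for both the assessment and the injection, treating the scheduled Week 52 assessments as pre-dose would agree with the order of procedures in the documents.

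The cost is a sentence or two in the SAP and one programming rule. No new data are needed and no efficacy analysis changes.

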Should a treatment gap exist between the Core and Extension Phase due to a delay of HA/EC approvals or other administrative/logistical reasons, the subject may enter the Extension Phase at a later time. During this treatment gap, the patient would remain in the main study and is allowed to be treated with any medication as deemed appropriate by the investigator to manage the patient's migraines. Upon HA and EC approval of the Extension Phase, the patient will then be administered study drug corresponding to the Week 52 dose and will continue dosing every 4 weeks as per protocol. Patients will be required to follow all protocol requirements for treatments allowed and for prohibited medications ([Section 6.2.2](#)).

End of Trial will occur when the last subject completes their last visit (LPLV) of the study.

Note: Treatment discontinuation does not imply study discontinuation. Every effort should be attempted to ensure subjects complete the study visits event if treatment is discontinued. After study completion, post-trial access to erenumab will be offered to the study participants as needed.

The primary analysis will occur when the last patient completes the Core Phase, prior to the end of the Extension Phase. The main study report will be prepared and finalized at this time for all data from the Core Phase.

An additional study report will be prepared for the Extension Phase after all patients have completed their respective last visit (LPLV) of the Extension Phase and will report data for the Extension Phase.

Figure 3-1 Study Design Schematic

¹ Dose adjustments may be done if allowed per label and is not a treatment failure. Switching to oral prophylactic in the erenumab arm or switching to a different oral prophylactic in oral prophylactic arm is allowed

² Treatment Discontinuation does not imply study discontinuation. Every effort should be attempted to ensure subjects complete the study visits even if treatment is discontinued.

³ Stratification based on Prior prophylactic migraine treatment - 1 prior treatment failure (70%) vs 2 prior treatment failures (30% cap)

⁴ "Eligible Core Phase Completers" are patients that complete visits through Week 52 on or off of study drug and are either benefitting from erenumab treatment or are in need of a treatment switch.

4 Rationale

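### SAP Table 2-2, rule 2.b.ii, lets the safety period run uncapped to the day before the first extension dose for a narrow group of subjects, and so counts the Core-to-Extension gap as treatment time

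*SAP*

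**What the plan says.** SAP 2.1.1.6, Table 2-2, defines the intervals for safety analysis. Rule 2 of the core row covers this group: "Subject completes 52 weeks on core phase but discontinues treatment early i.e. core phase treatment disposition reason is not equal to" COMPLETED. Its last branch, 2.b.ii, is for those who go on to PTA and whose Week 52 visit is no later than "treatment end date plus 27/1 day then use a day prior to first dose in PTA phase". The initially assigned and switched rows repeat that branch.

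Three neighbouring rules end the period earlier:

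- Rule 1.b.ii (treatment completed, delayed PTA entry): "Subject enters PTA phase after week 52 then use week 52 visit date".
- Rule 2.a.ii (same date condition, no PTA): "if week 52 visit date <= treatment end date plus 27/1 day then use week 52 visit date".
- Rule 2.b.i (PTA entrant whose Week 52 visit is later than treatment end plus 27/1 days): the period ends at treatment end plus 27/1 days.

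The safety follow-up row starts the day after core phase end. Its end is: "If subject enters PTA phase then use a day prior to first dose in PTA phase".

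A delay before PTA is foreseen. Protocol Section 3 says: "During this treatment gap, the patient would remain in the main study and is allowed to be treated with any medication". SAP 1.1 repeats this, and neither document sets a maximum length. SAP 2.8 reports safety by initially assigned treatment group unless otherwise specified.

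**The concern.** Rule 2.b.ii is the only branch that carries the treatment period across the gap. Rule 1.b separates PTA entry on the Week 52 date from later entry, and 2.b.ii lacks that split. An adverse event during the gap, on whatever drug the subject is then taking, would be placed in the core period. For a non-switcher it would be attributed to the initially assigned treatment. For a switcher, rule 4 of the initially assigned row has already closed that period the day before the first switch, so the event would go to the switched period.

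There may also be a mismatch of events and time. SAP 2.8.1 plans exposure-adjusted incidence rates. Exposure duration in SAP 5.6 ends at last injection plus 27 days for erenumab and at the last dose for oral drugs, so it leaves out the gap. If the rates use that duration as denominator, gap events enter without matching time. SAP 2.8.1 does not name the denominator, so this is conditional.

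No efficacy endpoint is affected.

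**Working it through.** The plan gives no figure to reproduce. The check applies the date rules of Table 2-2 to example dates.

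**Inputs.** Week 52 visit on Day 364 (target day, SAP Table 2-1). I read 27/1 as 27 days for erenumab and 1 day for oral drugs. Gap = first PTA dose day minus Week 52 day. The documents give no gap length, so 28, 84 and 168 days are assumptions. Disposition is not COMPLETED and the subject enters PTA.

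**Which branch applies.**

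- Erenumab, treatment end Day 337: 337 + 27 = 364. The visit is not later than this, so 2.b.ii applies.
- Erenumab, treatment end Day 336: 336 + 27 = 363. The visit is later, so 2.b.i applies and the period ends on Day 363.
- Oral, treatment end Day 363: 363 + 1 = 364, so 2.b.ii applies.
- Oral, treatment end Day 362: 362 + 1 = 363, so 2.b.i applies and the period ends on Day 363.

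**Period end under 2.b.ii** = 364 + gap − 1, the same in both arms:

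| Gap (days) | End under 2.b.ii | Days past Week 52 | End under 1.b.ii or 2.a.ii | End under 2.b.i (treatment end one day earlier) |
|---|---|---|---|---|
| 28 | Day 391 | 27 | Day 364 | Day 363 |
| 84 | Day 447 | 83 | Day 364 | Day 363 |
| 168 | Day 531 | 167 | Day 364 | Day 363 |

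A one-day change in treatment end therefore moves the period end by the full gap: 447 − 363 = 84 days, or 531 − 363 = 168 days. With no gap, 2.b.ii gives 364 − 1 = Day 363, the same as rule 1.b.i, so the fault appears only when PTA entry is delayed.

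**Safety follow-up.** With an 84-day gap it starts on 447 + 1 = Day 448 and ends on Day 447, so it has no days. Every gap length gives the same result.

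**Exposure against event window, 84-day gap, first dose on Day 1.** Erenumab exposure is 337 + 27 − 1 + 1 = 364 days, against an event window of 447 days, leaving 83 days unmatched. Oral exposure is 363 − 1 + 1 = 363 days against 447, leaving 84 days unmatched.

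**Protocol 12.5.2 window (112 days after last administration).** Erenumab: 337 + 112 = Day 449. Oral: 363 + 112 = Day 475. An 84-day gap ends inside both. A 168-day gap runs past them by 531 − 449 = 82 days and 531 − 475 = 56 days.

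**The case against.** The strongest reply is that this is a drafting slip in a rarely used branch. Three conditions must hold together: disposition not COMPLETED, Week 52 visit within 27 days (erenumab) or 1 day (oral) of treatment end, and PTA entry after Week 52. Treatment completers with a gap and subjects who stopped earlier are not touched. This stands. The point should not be read as covering every subject with a gap.

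A reader might infer that the rule loads events onto the oral arm, because oral entrants to PTA must need a treatment switch. The documents do not support that. Needing a switch is an eligibility judgement for PTA (Protocol Section 3), not a disposition code. To reach 2.b.ii, an oral subject must have dosed to within a day of the Week 52 visit and still not be COMPLETED. Yet the last planned oral dose is at Week 52, so such a subject would ordinarily be coded as completed. The erenumab date condition is wider, but a subject injected at Week 48 has also had the last planned core dose. Nothing says how either would be coded.

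A reader might also want to express the gap as a share of oral-arm time. The inputs are missing, and the date condition limits the count. If one-year persistence on the initial oral drug were 15% (an assumption), 0.15 × 197 = about 30 planned oral subjects would still be dosing on it at one year. Only those among them not coded COMPLETED and entering PTA late could qualify in the initially assigned row.

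Rule 3 may look like a companion fault, since it ends the period early: "use min(trt disposition date, trt end date plus 27/1 day". It concerns different subjects, who have no Week 52 visit and did not complete the study. Their later events still fall in safety follow-up, which runs to study disposition. I do not count it as an error.

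Finally, the protocol's 112-day window would itself treat much of a gap as on-treatment. But that limit is fixed and the same for everyone, whereas 2.b.ii has no limit and applies to one branch. Table 2-2 does not use the 112-day window, which needs reconciling in its own right.

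**Conclusion.** The inconsistency is real and follows from the text alone. For the subjects it covers, rule 2.b.ii gives a safety window that is out of line with 1.b.ii, 2.a.ii and 2.b.i, and it empties the interval meant to hold the gap. Per subject, the excess past Week 52 is the gap length minus one day: 27, 83 or 167 days for the assumed gaps. How many subjects are affected is unknown and probably small, and the direction between arms cannot be determined from the documents. The distortion of exposure-adjusted rates depends on whether they use the SAP 5.6 duration. The case for correction rests on the contradiction between rows of one table, not on a claim of material bias.

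**What to change.** In the core, initially assigned and switched rows of Table 2-2, replace 2.b.ii with the split already used in 1.b. If PTA starts on the Week 52 visit date, end the period the day before. If it starts later, end it on the Week 52 visit date. In the 84-day example the end moves from Day 447 to Day 364, and safety follow-up becomes Days 365 to 447 (83 days). Gap events are then still reported, under safety follow-up.

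Reconcile Table 2-2 with the 112-day on-treatment period in Protocol 12.5.2. SAP Section 4 declares no change to protocol-specified analyses, so either the windows should agree or the departure should be stated there. Name the denominator of the exposure-adjusted rates in SAP 2.8.1, so that events and time cover the same interval.

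The cost of the Table 2-2 correction is SAP wording and one date derivation, with no new data and no change to trial conduct. The reconciliation and the denominator statement also need only SAP text, unless the sponsor chooses to adopt the 112-day window, which would change the derivation for all subjects.
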